#### 6. DOSING DELAYS/DOSE MODIFICATIONS

Every effort should be made to administer study drugs according to the planned dose and schedule.

Patients whose treatment is delayed due to adverse events should be evaluated at intervals of one week or less until adequate recovery has been documented or no further improvement is expected. Dose delays will be made as indicated in the following table(s). In the event of multiple toxicities, dose modifications should be based on the worst observed toxicity. Patients must be instructed to notify Investigators at the first occurrence of any adverse symptom/s.

Treatment modification recommendations should be followed unless previously discussed with and agreed by the study chair. All dose modifications/adjustments must be clearly documented in the patient's notes and in the CRF. The descriptions and grading scales found in the revised NCI Common Terminology Criteria for Adverse Events (CTCAE) version 5.0 will be utilized for dose delays and dose modifications. A copy of the CTCAE version 5.0 can be downloaded from the CTEP website: http://ctep.cancer.gov/protocolDevelopment/electronic\_applications/ctc.htm.

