**Table 2 Management of Immune-Related Adverse Events** 

Gastrointestinal irAEs			
Severity of Diarrhea/Colitis (NCI-CTCAE v4)	Initial Management	Follow-up Management	
Grade 1 Diarrhea: < 4 stools/day over Baseline Colitis: asymptomatic	Continue immunotherapy agent(s)  Symptomatic treatment (e.g. loperamide)	Close monitoring for worsening symptoms Educate subject to report worsening immediately If worsens: Treat as Grade 2 or 3/4.	
Grade 2 Diarrhea: 4 to 6 stools per day over Baseline; IV fluids indicated < 24 hours; not interfering with ADL Colitis: abdominal pain; blood in stool	Withhold all immunotherapy agents Symptomatic treatment	If improves to Grade ≤ 1: Resume immunotherapy agents  If persists > 5-7 days or recurs: Treat as Grade 3 or 4.	
Grade 3 to 4 Diarrhea (Grade 3): ≥ 7 stools per day over Baseline; incontinence; IV fluids ≥ 24 h; interfering with ADL Colitis (Grade 3): severe abdominal pain, medical intervention indicated, peritoneal signs Grade 4: life-threatening, perforation	Withhold all immunotherapy agents for Grade 3. Permanently discontinue immunotherapy agents  1.0 to 2.0 mg/kg/day prednisone IV or equivalent Add prophylactic antibiotics for opportunistic infections Consider lower endoscopy	If improves: Continue steroids until Grade ≤ 1, then taper over at least 1 month;  If worsens, persists > 3 to 5 days, or recurs after improvement: Add infliximab 5mg/kg (if no contraindication). Note: infliximab should not be used in cases of perforation or sepsis.	

Dermatological irAEs			
Grade of Rash (NCI-CTCAE v4)	Initial Management	Follow-up Management	
Grade 1 to 2 Covering ≤ 30% body surface area or >30% of body surface area with mild symptoms only	Continue immunotherapy agent(s) Symptomatic therapy (for example, antihistamines, topical steroids)	If persists > 1 to 2 weeks or recurs: Withhold all immunotherapy agents Consider skin biopsy Consider 0.5-1.0 mg/kg/day prednisone or equivalent. Once improving, taper steroids over at least 1 month, consider prophylactic antibiotics for opportunistic infections, and resume immunotherapy agents following steroids taper.  If worsens: Treat as Grade 3 to 4.	

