Grade 2 AST or ALT > 3.0 to $\leq$ 5 x ULN and/or total bilirubin > 1.5 to $\leq$ 3 x ULN	Withhold all immunotherapy agents Increase frequency of monitoring to every 3 days.	If returns to Grade ≤ 1: Resume routine monitoring; resume immunotherapy agents.  If elevation persists > 5 to 7 days or worsens: Treat as Grade 3 to 4.

Grade 3 to 4 AST or ALT > 5 x ULN and/or total bilirubin > 3 x ULN	immunotherapy agents Increase frequency of monitoring to every 1 to 2 days 1.0 to 2.0 mg/kg/day prednisone or equivalent (Use 2.0 mg/kg for grade 4 hepatic irAEs) Add prophylactic antibiotics for opportunistic infections	If returns to Grade ≤ 1:  Taper steroids over at least 1 month.  If does not improve in > 3 to 5 days, worsens or rebounds:  Add mycophenolate mofetil 1 gram (g) twice daily  If no response within an additional 3 to 5 days, consider other immunosuppressants per local guidelines.		
	Renal irAEs			
Grade of Creatinine Increased (NCI-CTCAE v4)	Initial Management	Follow-up Management		
Grade 1 Creatinine increased > ULN to 1.5 x ULN	Continue immunotherapy agent(s)	Continue renal function monitoring If worsens: Treat as Grade 2 to 3 or 4.		
Grade 2 to 3 Creatinine increased > 1.5 and ≤ 6 x ULN	Withhold all immunotherapy agents Increase frequency of monitoric to every 3 days 1.0 to 2.0 mg/kg/day prednison or equivalent. Add prophylactic antibiotics fo opportunistic infections Consider renal biopsy	steroids taper.  le  If worsens:		
Grade 4 Creatinine increased > 6 x ULN	Permanently discontinue all immunotherapy agents Monitor creatinine daily 1.0 to 2.0 mg/kg/day prednison or equivalent.	If returns to Grade ≤1:  Taper steroids over at least 1 month.		

	Add prophylactic antibiotics for opportunistic infections Consider renal biopsy Nephrology consult	
	Cardiac irAEs	
Myocarditis	Initial Management	Follow-up Management

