Grade 3 or Grade 4 thyroid endocrinopathies (hypothyroidism, hyperthyroidism)  Grade 3 (diabetes mellitus/hyperglycemia)	Withhold all immunotherapy agents Consider hospitalization Endocrinology consult  Start thyroid hormone replacement therapy (for hypothyroidism), anti-thyroid treatment (for hyperthyroidism), or insulin (for type I diabetes mellitus) as appropriate.  Rule-out secondary endocrinopathies (i.e. hypopituitarism /	Resume all immunotherapy agents once symptoms and/or laboratory tests improve to Grade ≤ 1 (with or without hormone replacement/suppression).  Continue hormone replacement/suppression and monitoring of endocrine function as appropriate.  For any symptomatic endocrine reactions lasting > 6 weeks, permanently discontinue both immunotherapy agents.	

	hypophysitis)	
Grade 3 or Grade 4 adrenal insufficiency  Grade 4 diabetes mellitus/hyperglycemia	Permanently discontinue all immunotherapy agents.  Consider hospitalization Endocrinology consult	Continue hormone replacement/suppression and monitoring of endocrine function as appropriate.
	Start corticosteroid replacement (for adrenal insufficiency) or insulin (for type I diabetes mellitus) as appropriate.  Rule-out secondary endocrinopathies (i.e. hypopituitarism / hypophysitis)	
Grade 1-3 Hypopituitarism/Hypophysitis (secondary endocrinopathies)	If secondary thyroid and/or adrenal insufficiency is confirmed (i.e. subnormal serum FT4 with inappropriately low TSH and/or low serum cortisol with inappropriately low ACTH):  • Refer to endocrinologist for dynamic testing as indicated and measurement of other hormones (FSH, LH, GH/IGF-1, PRL, testosterone in men, estrogens in women)  • Hormone replacement/suppressive therapy as appropriate  • Perform pituitary MRI and visual field examination as indicated  If hypophysitis confirmed:	Resume all immunotherapy agents once symptoms and hormone tests improve to Grade ≤ 1 (with or without hormone replacement).  In addition, for hypophysitis with abnormal MRI, resume avelumab only once shrinkage of the pituitary gland on MRI/CT scan is documented.  Continue hormone replacement/suppression therapy as appropriate.  For any symptomatic endocrine reactions lasting > 6 weeks, permanently discontinue both immunotherapy agents.
	If hypophysitis confirmed:	

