Grade 4 Hypopituitarism/Hypophysitis	
 
Continue all immunotherapy agents if mild symptoms with normal MRI. Repeat the MRI in 1 month
 
Withhold all immunotherapy agents if moderate, severe or lifethreatening symptoms of hypophysitis and/or abnormal MRI. Consider hospitalization. Initiate corticosteroids (1 to 2 mg/kg/day prednisone or equivalent) followed by corticosteroids taper during at least 1 month.
 
Add prophylactic antibiotics for opportunistic infections.
 
Permanently discontinue all immunotherapy agents.
 
	Continue hormone replacement/suppression and
(secondary endocrinopathies)	See additional recommendations for grade 1-3 hypophysitis above.	monitoring of endocrine function as appropriate.
	Ophthalmic irAEs	
Grade (NCI-CTCAE v4)	Initial Management	Follow-up Management
Grade 1	Continue immunotherapy agent(s)	Continue monitoring If worsens: Treat as Grade 2 to 3 or 4.
Grade 2 to 4 Creatinine increased > 1.5 and ≤ 6 x ULN	Withhold all immunotherapy agents Increase frequency of monitoring to every 3 days  Initiate topical therapy and/or 1.0 to 2.0 mg/kg/day prednisone or equivalent. Add prophylactic antibiotics for opportunistic infections	If returns to Grade ≤1 within two weeks:  Taper steroids over at least 1 month, and resume immunotherapy agents following steroids taper.  If does not return to Grade ≤1 within two weeks: permanently discontinue all immunotherapy

		agents		
Other irAEs (not described above)				
Grade of other irAEs (NCI-CTCAE v5)	Initial Management	Follow-up Management		
Grade 2 or Grade 3 clinical signs or symptoms suggestive of a potential irAE	Withhold all immunotherapy agents pending clinical investigation	If irAE is ruled out, manage as appropriate according to the diagnosis and consider restarting all immunotherapy agents If irAE is confirmed, treat as Grade 2 or 3 irAE.		
Grade 2 irAE or first occurrence of Grade 3 irAE	Withhold all immunotherapy agents  1.0 to 2.0 mg/kg/day prednisone or equivalent  Add prophylactic antibiotics for opportunistic infections  Specialty consult as appropriate	If improves to Grade ≤ 1: Taper steroids over at least 1 month and resume all immunotherapy agents following steroid taper.		

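### Table 2 defines the Grade 2 to 4 ophthalmic row by a creatinine range and ties the pituitary-imaging restart condition to avelumab, which is not a study drug

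*Combined protocol and SAP*

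**What the plan says.** Section 6 makes the modification tables the default: they are to be followed unless something else has been agreed with the study chair. Section 6.4 refers resumption of treatment to Tables 2 to 4. Section 6.2 counts uveitis and iritis among the eye events and lets the treating physician's judgment override Table 2.

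Within Table 2:

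- **Ophthalmic block.** The row above Grade 1 is labelled and defined as "Grade 2 to 4 Creatinine increased > 1.5 and ≤ 6 x ULN". Its actions include "Initiate topical therapy and/or 1.0 to 2.0 mg/kg/day prednisone or equivalent" and a time limit: "If does not return to Grade ≤1 within two weeks: permanently discontinue all immunotherapy".
- **Renal block.** The corresponding row is "Grade 2 to 3 Creatinine increased > 1.5 and ≤ 6 x ULN", followed by a separate row, "Grade 4 Creatinine increased > 6 x ULN".
- **Endocrine block, Grade 1 to 3 hypopituitarism/hypophysitis.** All agents may resume once symptoms and hormone tests improve to Grade 1 or less. A further sentence, for hypophysitis with an abnormal MRI, says "resume avelumab only once shrinkage of the pituitary gland on MRI/CT scan is documented".

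On grading, Section 6 states that CTCAE "version 5.0 will be utilized for dose delays and dose modifications", while most of the Table 2 column headings that name a version name v4.

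**The concern.** These cells tell a site when to hold both drugs, when to stop them for good and when to restart. An eye-event row whose only printed criterion is a kidney test does not describe the events it is meant to govern. A restart condition attached to a drug outside the study places no literal condition on the drugs inside it.

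Section 12.3 and Appendix B provide for external sites, and Appendix B requires departures from defined procedures to be reported. If a rule does not say what it means, two sites can handle the same event differently, and it is unclear which of them has departed from the protocol. What is at stake is patient safety, treatment exposure and consistent discontinuation decisions. The test of the objective response rate is not at stake.

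**Working it through.** No arithmetic applies, so the check compares passages.

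**1. Ophthalmic rows against renal rows (Table 2)**

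| Element | Renal | Ophthalmic |
|---|---|---|
| Grade 1 criterion | Creatinine above ULN, up to 1.5 x ULN | None printed |
| Next row | "Grade 2 to 3 Creatinine increased > 1.5 and ≤ 6 x ULN" | "Grade 2 to 4 Creatinine increased > 1.5 and ≤ 6 x ULN" |
| Separate Grade 4 row | "Grade 4 Creatinine increased > 6 x ULN" | None |
| Distinctive action | Consider renal biopsy | Topical therapy as an option |
| Two-week stopping rule | None visible | Yes |

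Four things follow.

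- An eye event with normal creatinine does not meet the printed criterion for the ophthalmic Grade 2 to 4 row.
- A creatinine of, say, 3 x ULN satisfies the printed criterion of both the renal and the ophthalmic row. Only the block heading separates them.
- The ophthalmic label includes Grade 4, but its range ends at 6 x ULN, which is where renal Grade 4 begins. The row therefore disagrees with the table's own creatinine grading.
- This is unlikely to be text displaced when the PDF was read. The label (2 to 4) differs from the renal label (2 to 3), and the row has its own eye-specific action and time limit. The ophthalmic Grade 1 cell also refers to a split between Grade 2 to 3 and Grade 4 that exists only in the renal block. The pattern suggests renal text that was copied and only partly edited.

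**2. Hypophysitis: hold rule against release rule**

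- *Hold.* Moderate or worse symptoms, or an abnormal MRI, or both, lead to withholding all agents. An abnormal MRI is enough.
- *Release, first sentence.* All agents resume on symptoms and hormone tests.
- *Release, second sentence.* For an abnormal MRI, an imaging condition is added, but for avelumab.
- *Study drugs.* Section 1.1 names ipilimumab with or without nivolumab. Section 5.4.5 bars other investigational agents. Avelumab appears nowhere else in the protocol.

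Take a patient held for an abnormal MRI whose symptoms and hormone tests are back to Grade 1 or less, but whose pituitary has not yet been shown to shrink. Read literally, both drugs may restart. If the drug name is taken as a slip for one or both study drugs, the imaging condition still blocks restart of whichever drug is meant. The text does not settle which reading applies.

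**3. CTCAE version**

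Six Table 2 headings name v4: gastrointestinal, rash, pneumonitis, liver tests, creatinine and ophthalmic. The heading for other events names v5. The cardiac and endocrine headings name none. Section 6 says version 5.0 governs dose delays and modifications, and Sections 5 and 7.2 also use version 5.

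**The case against.** The best reply is that the table still works in practice. The eye row sits under an ophthalmic heading and carries a CTCAE grade label, so a site can grade the eye event and ignore the creatinine text. The avelumab sentence is worded as an addition to the one before it, so a sensible reader would carry the imaging condition over to the study drugs. Section 6.4 has all study drugs delayed together, which limits drug-by-drug readings. Section 6.2 allows physician override, and Section 6 allows agreement with the study chair.

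Much of this stands. A reader might infer that the rows cannot be used at all, or that a creatinine rise would in practice be managed under two rows. The documents do not support either. The block headings separate kidney from eye, and the initial actions largely coincide: withhold, monitor every 3 days, steroid in the same dose range, prophylactic antibiotics.

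What does not stand is the step from workable to correct. Each workaround requires the site to disregard printed text, and discretion to override a rule does not make the rule readable.

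A reader might also infer a third error in the Grade 3 to 4 colitis cell, which says "Withhold all immunotherapy agents for Grade 3. Permanently discontinue immunotherapy agents". That cannot be relied on. The row covers two grades, and other cells of the table are visibly truncated in the available text (the hepatic Grade 3 to 4 action cell begins mid-sentence), so a grade qualifier may simply have been lost.

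**Conclusion.** The point holds for two rules in Table 2. The ophthalmic Grade 2 to 4 row carries the renal creatinine range, and the pituitary-imaging restart condition names a drug that is not in the study. Both are drafting errors in an operative safety table and should be corrected. The CTCAE mismatch is real but secondary: many rows print their own criteria, and the documents do not show an event that would be graded differently under the two versions.

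No patient count should be attached. A reader might apply the 13% hypophysitis rate quoted in Section 2.2.4 to the 13 planned patients. That rate comes from an adjuvant trial at 10 mg/kg, the same section says immune-related event rates are lower at 3 mg/kg, and only Grade 1 to 3 cases with an abnormal MRI reach the avelumab sentence. The documents give no rate for that subset.

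The primary test (4 or more responses among 13 patients) does not use Table 2, and neither its error rate nor its power changes. The conclusion assumes that the creatinine text and the drug name stand in the source document as they do here, which the internal evidence supports.

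**What to change.** Amend Table 2 in one pass:

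- Reconcile the ophthalmic Grade 2 to 4 row with the renal rows and with the eye events named in Section 6.2, and align the cross-reference in the ophthalmic Grade 1 cell with the rows that exist in that block.
- Reconcile the pituitary-imaging condition with the study drugs, so that it is clear whether and to which agents it applies and how it relates to the preceding resumption sentence.
- As a side correction, reconcile the CTCAE v4 headings with the version 5.0 rule in Section 6.

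The clinical team must decide the content of each rule; none is proposed here. The cost is one table correction by amendment, with notice to sites. Sample size, endpoints and the analysis do not change.

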## **6.3** Non-Immune Related Adverse Events

Dose delays for drug-related non-immune related toxicities related to ipilimumab and nivolumab are detailed in Table 2 and Table 3. The treatment modifications detailed in these tables should be followed for both ipilimumab and nivolumab.

**Table 3 Treatment Modifications for Non-Immune Treatment-Related Hematologic Toxicities** 

	Treatment modification
Grade 1	Continue per schedule
Grade 2	Continue per schedule
Grade 3 Thrombocytopenia	Withhold study treatment and provide growth factor or transfusion support if indicated until return to grade 2 or baseline level; if returns to grade 2 or less within 7 days, resume study treatment (first occurrence only). If the AE does not return to grade 2 or baseline level in 7 days or recurs after re-initiation of study therapy, we recommend a diligent search for alternative causes and consideration of discontinuation in consultation with study chair.
Other Grade 3 Cytopenias	Continue per schedule
Grade 4	Withhold study treatment and provide growth factor or transfusion support if indicated until return to grade 2 or baseline level; if returns to grade 2 or less within 7 days, resume study treatment (first occurrence only). If the AE does not return to grade 2 or baseline level in 7 days or recurs after re-initiation of study therapy, we recommend a diligent search for alternative causes and consideration of discontinuation in consultation with study chair.

Table 4 Treatment Modifications for Treatment-Related Non-Hematologic Toxicities

Non-Hematologic	Treatment modification
Toxicity	
Grade 1	Continue per schedule
Grade 2	Continue per schedule
Grade 3	First occurrence: Withhold until return to grade 1 or baseline level; re-
	initiate therapy (after discussion with study chair). For recurrent grade 3
	AEs, permanently discontinue both immunotherapy agents
Other-Grade 4	Permanently discontinue*
irAEs	See Table 2
Infusion-related	See Section 6.6
reactions	

\*For asymptomatic grade 4 laboratory abnormalities including lipase, amylase, CK elevations, the subject may be restarted on treatment if the abnormality resolves to grade 1 or baseline, in cases where the investigator judges that the benefit of resuming treatment outweighs the risk, and after discussion with the Study Chair.

# 6.4 Treatment Delays

Treatment should be delayed per Tables 2-4 or based on any adverse event, laboratory abnormality, or condition that, in the judgment of the investigator, warrants delaying the dose of study medication. If a dose delay is necessary, all study drugs must be delayed until treatment can resume.

Subjects should resume treatment per Tables 2-4. Subjects must be re-treated within 6 weeks from the previous dose. Treatment may be resumed after 6 weeks after discussion with the Study Chair if the benefit/risk justify continuing study therapy. At least 19 days must elapse between the replacement dose of study therapy and administration of the subsequent dose of study therapy. In the case of endocrine-related AEs, hormone replacement therapy may be utilized to restore physiologic function and to permit retreatment with study drug. If this is not possible the subject must be discontinued from study therapy.

#### 6.5 Dose Reductions

No dose reductions are permitted for ipilimumab or nivolumab.

# 6.6 Management of Infusion-Related Reactions

Infusion reactions with ipilimumab and nivolumab are rare and no empiric premedication is recommended. If an infusion related reaction occurs following infusion, managed guidelines are outlined in Table 5. Symptoms may include one or more of the following: fever, chills, rigors, diaphoresis, and headache.

Once the infusion rate has been decreased by 50% due to an infusion-related reaction, the same decreased infusion rate must be used for all subsequent infusions.

**Table 5 Treatment Modifications for Symptoms of Infusion Related Reactions** 

NCI-CTCAE Grade	Treatment Modification for ipilimumab and/or nivolumab
Grade 1 – mild  • Mild transient reaction; infusion interruption not indicated; intervention not indicated	Decrease the infusion rate by 50% and monitor closely for any worsening

 
Grade 2 – moderate
 
Therapy or infusion interruption indicated but responds promptly to symptomatic treatment (for example, antihistamines, NSAIDs, narcotics, IV fluids); prophylactic medications indicated for ≤ 24h
 
	
 
Temporarily discontinue infusion
 
Resume infusion at 50% of previous rate once infusion-related reaction has resolved or decreased to at least Grade 1 in severity, and monitor closely for any worsening
 

Grade 3 or Grade 4 – severe or life-threatening  • Grade 3: Prolonged (for example, not rapidly responsive to symptomatic medication and/or brief interruption of infusion); recurrence of symptoms following initial improvement; hospitalization indicated for clinical sequelae  • Grade 4: Life-threatening consequences; urgent intervention indicated	
 
Stop the infusion immediately and disconnect infusion tubing from the subject
 
Subjects cannot receive any further treatment with the offending agent.
 

IV: intravenous; NCI-CTCAE: National Cancer Institute-Common Terminology Criteria for Adverse Event; NSAIDs: nonsteroidal anti-inflammatory drugs.

# 6.6.1 Additional Treatment Modifications for Patients with Grade 2 Infusion-Related Reactions

In the event of a Grade 2 infusion-related reaction that does not improve or that worsens following implementation of the modifications indicated in Table 5 (including reducing the infusion rate by 50%), the Investigator may consider treatment with corticosteroids per local guidelines, and the infusion should be stopped for that day. At the time of the next cycle, the following prophylactic pre-medications are recommended for future infusions: diphenhydramine 50 mg (or equivalent) and paracetamol 325 to 1000 mg (acetaminophen) at least 30 minutes before additional study drug administrations.

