### 5.4.1 Pre-medications

No pre-medications are required with this regimen, unless the patient experiences an infusion-related reaction (see Section 6.4).

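### Section 6.6.1 foresees further infusions after some reactions that Table 5's own definitions make Grade 3 and bar from re-treatment

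*Combined protocol and SAP*

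**What the plan says.** Table 5 (Section 6.6) sets grade definitions and actions for infusion reactions to either drug.

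- **Grade 2, definition:** "Therapy or infusion interruption indicated but responds promptly to symptomatic treatment".
- **Grade 2, action:** interrupt, then "Resume infusion at 50% of previous rate once infusion-related reaction has resolved or decreased to at least Grade 1 in severity".
- **Grade 3, definition (relevant part):** "Prolonged (for example, not rapidly responsive to symptomatic medication and/or brief interruption of infusion); recurrence of symptoms following initial improvement".
- **Grade 3 or 4, action:** stop at once, and "Subjects cannot receive any further treatment with the offending agent".

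Section 6.6.1 adds instructions for "a Grade 2 infusion-related reaction that does not improve or that worsens following implementation of the modifications indicated in Table 5", and names the 50% rate reduction among those modifications. Corticosteroids may be considered, and "the infusion should be stopped for that day". It continues: "At the time of the next cycle, the following prophylactic pre-medications are recommended for future infusions".

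Section 5.4.1 says that pre-medication is not required "unless the patient experiences an infusion-related reaction (see Section 6.4"). Section 6.4 is headed Treatment Delays and does not mention pre-medication.

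**The concern.** Table 5 uses promptness of response, and absence of recurrence, to separate Grade 2 from Grade 3. Section 6.6.1 is written for reactions in which the Grade 2 measures have not worked, yet it keeps the Grade 2 label and the route to further dosing. If such a reaction is already Grade 3 under Table 5, one paragraph closes off the drug and the next plans for its return.

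Three things are at stake:

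- **Safety.** Whether a patient is re-exposed after a reaction that Table 5 calls severe would depend on which text the treating site follows.
- **Consistency.** The protocol provides for external sites (Sections 4.3 and 4.4, Appendix B), and two sites could grade and manage the same event differently in good faith.
- **Reported toxicity.** Sections 1.3 and 13.4 make the rate of grade 3 or higher toxicity a secondary endpoint, both regardless of attribution and when at least possibly related. The choice between Grade 2 and Grade 3 feeds both rates.

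**Working it through.** The plan gives no figure on this point, so the check is a comparison of texts.

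**Step 1. Sort the reactions that Section 6.6.1 can cover by when they fail, and read each against Table 5.**

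| Course of a reaction first graded 2 | Table 5 reading | Conflict? |
|---|---|---|
| No improvement after interruption and symptomatic treatment | Fails the Grade 2 condition of prompt response; meets the first Grade 3 limb | Yes |
| Worsens before any restart | Has not responded to the measures; meets the first Grade 3 limb, or a higher grade | Yes |
| Settles, restarts at half rate, then worsens or recurs | Restart is allowed only after resolution or a fall to Grade 1, so there was initial improvement; meets the second Grade 3 limb | Yes |
| Falls to Grade 1, restarts at half rate, residual Grade 1 symptoms simply persist | Did respond, and nothing has come back; Grade 3 not clearly met | Not necessarily |

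**Step 2. Compare the actions for the three conflicting rows.** Table 5 permits no more of the drug responsible. Section 6.6.1 ends that day's infusion and recommends pre-medication before later ones. It foresees re-treatment without expressly ordering it, but advice on pre-medicating later infusions has no use if there can be none.

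**Step 3. Look for a clause that settles the matter.**

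- Table 4 sends infusion reactions to Section 6.6, so the conflict lies inside the governing section.
- The opening of Section 6 adopts CTCAE version 5.0 grading and lets the study chair agree departures. It does not say whether Table 5 or Section 6.6.1 is the default.
- Section 6.7 allows the other drug to continue. It says nothing on resuming the one that caused the reaction. Under Table 1 in Section 5.1, ipilimumab is the only drug given in induction and maintenance, so reading Section 6.6.1 as referring to the other drug cannot help there.
- Section 6.6.2 covers symptom management in severe hypersensitivity and does not address re-treatment.

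**Step 4. Effect of one label on the toxicity endpoint.** With the 13 planned patients all treated, one patient moved between Grade 2 and Grade 3 changes the rate of grade 3 or higher toxicity by 1/13 = 0.077, or 7.7 percentage points, provided that the patient has no other qualifying event. The third safety rate, grade 2 or higher and at least probably related, is unaffected, because either label counts. This shows what one patient is worth; it does not forecast how many there will be.

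**The case against.** The strongest reply is that Section 6.6.1 is, by its heading, about Grade 2 only. Since Section 6 adopts CTCAE grading throughout, a reaction that becomes Grade 3 would leave Section 6.6.1 and enter the Grade 3 or 4 row of Table 5. Table 5 also leaves its terms for promptness and brevity undefined, so the boundary is the investigator's judgement, and residual Grade 1 symptoms at half rate could be what Section 6.6.1 has in mind.

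Part of this stands. The last row of the table above is a real exception, so it would be too strong to say that everything in Section 6.6.1 is Grade 3. The rest does not remove the conflict. Section 6.6.1 does not limit itself to residual Grade 1 symptoms: it says Grade 2, and it expressly includes worsening. Nor does it tell the site to regrade and move to the other row.

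Three stronger readings are tempting, and the documents do not support them.

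- **A count of affected patients.** A reader might apply the 4-20% listed for ipilimumab infusion reactions in Section 7.1.1.1 to 13 patients. That range has no grade limit, whereas the group in question is a subset of Grade 2 reactions whose share is not given. Section 6.6 itself describes infusion reactions to these drugs as rare.
- **A loss of power or a shift in the primary response rate.** A reader might infer that a patient stopped after one dose cannot respond, and recompute the stated power of 0.83 with 12 patients. Section 2.4 reports complete responses in two of fourteen patients after a single ipilimumab dose in an earlier study, so the premise fails.
- **A third rule in Section 5.4.1.** Its general statement on pre-medication is compatible with Section 6.6. Only its section reference is wrong.

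**Conclusion.** The conflict is real but partial. For a reaction first graded 2 that fails to respond to interruption and symptomatic treatment, or that worsens or recurs after the half-rate restart, Table 5 and Section 6.6.1 give incompatible grades and incompatible consequences, and nothing elsewhere ranks them. It does not extend to mild symptoms that persist unchanged at half rate.

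The consequences are a safety conflict and a risk of inconsistent grading across sites, with a knock-on to the two grade 3 or higher toxicity rates. The number of patients concerned is not given and is likely small. No effect on power or on the primary response rate is claimed. The conclusion rests on two things: reading Table 5's definitions as written, and taking Section 6.6.1's pre-medication advice to mean that further infusions of the same drug are foreseen. No view is taken on which clinical instruction is right.

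**What to change.** Reconcile Section 6.6.1 with Table 5 so that a reaction that does not respond to interruption and treatment, or that worsens or recurs after the half-rate restart, carries one grade and one instruction on further treatment. The sponsor's clinical team must decide which instruction stands. The revised text should also say whether residual Grade 1 symptoms persisting at half rate fall under Section 6.6.1, since that is the one case the present wording can cover without contradiction. In Section 5.4.1, change the cross-reference from Section 6.4 to Section 6.6.

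The cost is protocol wording in Section 6.6.1, Section 5.4.1 and, if the team so decides, Table 5. It needs no additional patients, visits or data items.
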